**Table 2. Study Schedule**

Events	Visit 1	Visit 2	Visit 3	Visit 4	Visit 5	Visit 6	Visit 7
		First product		Second product		Third product	
Informed consent, demographics, Inclusion/Exclusion criteria, medical history, concurrent meds	X						
Update of Inclusion/Exclusion criteria	X*	X	X	X	X	X	X
Clinical endpoints (PI and Gingival Abrasion)		X	X	X	X	X	X
Digital dental photos		X	X	X	X	X	X
Test product distribution		X		X		X	
Instruction of brushing		X		X		X	
Clinical endpoints (PI and Gingival Abrasion) immediate post-brushing		X		X		X	
Digital dental photos immediate post-brushing		X		X		X	
Wash-out period products distribution (TP and TB)	X						
Used test product collection			X		X		X
Diary disbursement and collection		X					X
Compliance check			X		X		X
Adverse events		X	X	X	X	X	X

Note: Visit 1, 3 and 5 will be followed by a 1 week "washout" period.

\*Evaluation of PI (Quigley and Hein) is included.

Version 061020

## **VIII. CLINICAL SUPPLIES**

### **Test Materials**

The sponsor will provide the following items to the study site:

- 3 test toothbrushes with different types of bristles (A, **B**, C)
- Toothbrush for wash-out period
- Toothpaste throughout the study period

### **Packaging and Labeling**

The toothbrushes will be identically labeled by the sponsor.

### **Delivery and Inventory:**

Immediately upon receipt of study supplies at the clinical site, study personnel will account for all products. The study staffs are responsible to maintain the accountability log.

### **Storage:**

Study supplies will be maintained under secure conditions, until assignment to subjects.

### **Return of Study Supplies:**

At the conclusion of the study, all unused product will be returned to the Sponsor. Used products will also be returned to the Sponsor.

## **IX. TREATMENT REGIMEN**

Qualified subjects meeting all inclusion and exclusion criteria will be provided their assigned toothbrush (A, **B** or C) at Visit 2, 4 and 6 for use for immediate post-brushing evaluation and during the one-week treatment phase of the study. Subjects will be instructed to brush their teeth as instructed with their assigned toothbrush 2 times daily (after breakfast, before going to bed) for 2 minutes, using only the provided toothpaste for one-week study period.

Following their one week of use, they will then go through a one-week "washout" period and will follow their normal oral hygiene using study provided toothbrush and fluoride toothpaste. The same fluoride toothpaste will be used throughout the whole study period. Subjects will refrain from using other oral hygiene products throughout the study period.

Version 061020

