## III. STUDY OBJECTIVES

The primary objective of this study is to evaluate and compare toothbrushes with three different bristle types in the reduction of plaque index (**PI**) for interdental area and digitally measured interdental plaque area after one-time brushing.

Secondary objectives are to evaluate toothbrushes with three different bristle types in the changes of PI, digitally measured interdental plaque area and gingival abrasion one week after using the toothbrushes, and to assess an agreement between the different evaluation methods (**PI** and a plaque area by image analysis)

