## **XII. STUDY PROCEDURE**

### **Screening and Enrollment Visit (Visit 1)**

Potential subjects will be instructed to refrain from regular oral hygiene regimen for 24 hours and eating for 4 hours before the appointment in the study.

Male and female subjects will read and sign the informed consent prior to enrollment. Subjects will be asked about demographics, medical history, general health status and current medication usage, and the information will be recorded.

Plaque Index (Quigley and Hein) of a whole mouth will be evaluated to verify that the subjects meet the inclusion and exclusion criteria (average PI>2).

If the participants meet the study criteria, they will be assigned to one of three treatment groups randomly based on computer generated randomized numbers.

Subjects will be instructed to use a toothpaste and a toothbrush (for wash-out period) provided by the study staff until the next visit. The appointment of next visit will be scheduled within 7 days ± one day.

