### **Visit 2**

The following will happen at this visit:

Potential subjects will be instructed to refrain from regular oral hygiene regimen for 24 hours and eating for 4 hours before the appointment in the study. The study staff will

Version 061020

update of Inclusion/Exclusion Criteria, medical history, and concurrent medications.

Whole-mouth Plaque Index (Navy PI) and Gingival Abrasion Score will be evaluated by a qualified examiner following visualize dental plaque with a disclosing agent (Mira-2-Ton, Miradent) and record the scores on the Case Report Form for the baseline information. Successively, standardized dental digital photographs of three close-up views of the retracted views for plaque area measurement: front, left and right lateral sides.

Assigned toothbrush and a fluoride toothpaste will be given to each subject. the study staff will instruct Bass method to each subject (without using a toothbrush) and provide the assigned toothbrush with a half inch length of the toothpaste. Subjects will brush their teeth for 2 minutes with Bass method under a supervision of the study staff. Whole-mouth Navy PI and Gingival Abrasion Score will be recorded, and standardized dental digital photographs will be taken again for immediate post-brushing evaluation.

Subjects will then be instructed to use assigned product to use 2 times daily, after breakfast and before bedtime, for one week for 2 minutes with instructed brushing method. They will maintain a daily diary of their product usage. Compliance will be assessed by subject diary.

Next appointment will be scheduled within 7 days  $\pm$  one day. Subjects will be instructed to refrain from regular oral hygiene regimen for 24 hours and eating for 4 hours before the appointment in the study. They will be advised to follow the instructions carefully and return to the study center with their assigned toothbrush and diary for their next examination.

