### **Visit 3**

After one week, subjects will return to the office to return the used toothbrush and their dairy. The following will happen at this visit:

The study staff will update of inclusion/exclusion criteria, medical history and concurrent medications. Adverse experiences will be noted and recorded during the study.

Whole-mouth Navy Plaque Index and Gingival Abrasion Score will be evaluated by a qualified examiner following visualize dental plaque and record. Then, standardized dental digital photographs of three close-up views of the retracted views: front, left and right lateral sides.

Subjects will follow their normal oral hygiene using a toothbrush and a toothpaste for "wash-out" period given at Visit 1.

Next appointment will be scheduled to return within 7 days  $\pm$  one day, and subjects will be instructed to refrain from regular oral hygiene regimen for 24 hours and eating for 4 hours before the appointment in the study.

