## XVI. STATISTICAL ANALYSIS AND DATA MANAGEMENT

Since this study is a Proof of Concept study, the sample size calculation was not performed.

Descriptive statistics for all subjects will be performed for background and demographic variables. Continuous variables are expressed as frequencies (n), mean +/- SD and categorical variables are expressed as frequencies (n) and percentages (%).

Student *t* test or Wilcoxon *rank sum* test where appropriate, will be used to compare among different bristles. For intragroup changes of endpoints before/after one-time brushing or use for one-week, paired *t* test or Wilcoxon signed rank test will be used where appropriate. Spearman Rank Order Correlation was used to analyze correlations between the variables.

Safety parameters will include oral soft and hard tissues and subjective reports as well as any AEs. The analysis will include all observed effects which initially occurred or worsened following treatment. Any adverse effects will be summarized classified according to their intensity (mild, moderate, or severe) and relationship (definitely related, probably related, possibly related, probably not related or definitely not related) to study product.

All statistical tests will be conducted using Minitab 18.

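### The one-week change within each brush compares usual brushing with instructed Bass brushing, so the paired within-brush test cannot by itself show a brush effect

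*Combined protocol and SAP*

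**What the plan says.** **Weeks before the baselines (Visits 2, 4 and 6).** For the wash-outs, section IX says subjects "will follow their normal oral hygiene using study provided toothbrush and fluoride toothpaste". Section XII, Visit 3 agrees: "Subjects will follow their normal oral hygiene using a toothbrush and a toothpaste for" that period. Neither place sets a technique, frequency or duration. For the run-in week, section XII, Visit 1 says only: "Subjects will be instructed to use a toothpaste and a toothbrush (for wash-out period) provided by the study staff until the next visit". It does not use the word normal, but Table 2 counts this week as a wash-out ("Note: Visit 1, 3 and 5 will be followed by a 1 week" period of that kind), and no brushing instruction precedes it.

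**Start of each test week.** At Visit 2 the plaque and abrasion scores and the photographs come first. Then "the study staff will instruct Bass method to each subject (without using a toothbrush"), and supervised brushing follows. Visit 4 uses the same procedures, and Table 2 schedules instruction at Visits 2, 4 and 6.

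**Test weeks.** The assigned brush is used twice daily "for one week for 2 minutes with instructed brushing method". The instruction is the same for A, B and C.

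**Analysis.** Section III: "Secondary objectives are to evaluate toothbrushes with three different bristle types in the changes of PI", plaque area and gingival abrasion after one week. Section XV lists these changes as secondary outcomes 1, 2 and 4. Section XVI: "For intragroup changes of endpoints before/after one-time brushing or use for one-week, paired" t or signed rank tests will be used. It provides separately for a comparison among bristles, and does not say which of the two analyses carries the one-week conclusion.

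**The concern.** A paired before-and-after test supports a statement about the brush only if the brush is what changed. Here the week before baseline is brushed in the subject's own way with a wash-out brush that section VIII does not describe. The week before the one-week score is brushed with a taught technique and a set regimen. A fall in plaque within a brush could come from the instruction alone. So could a rise in gingival abrasion, which would then be read as a safety signal for the bristle.

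What is at stake is a sentence in the report such as: brush A reduced interdental plaque significantly over one week. The plan permits that sentence, and the design cannot support it.

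**Working it through.** The plan gives no alpha, SD or effect size and no sample size calculation, so there is no stated figure to reproduce. The check asks how often the within-brush test would be significant if the brush did nothing.

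**Inputs.** n = 10 (section VI). Sequences ABC, BCA and CAB (section VII). Assumptions: two-sided 5% level, brush effect zero, independent normal changes with SD 1, and a technique shift d of 0.3, 0.5, 0.8 or 1.0 SD of the within-subject change. The documents give no value for d.

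**Case 1: the shift recurs in full in every period** (subjects return to their own habits in each wash-out). The paired t statistic is noncentral t with 9 degrees of freedom and noncentrality d√10. The critical value is 2.262.

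**Case 2: the shift occurs only in period 1** (technique learned at Visit 2 is kept, so later baselines already contain it). Each brush comes first in one sequence. If 10 subjects split 4/3/3, then 3 or 4 of the 10 changes for a given brush carry the shift. Rejection rates are by simulation.

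| d (SD) | Noncentrality d√10 | Case 1, all 10 shifted | Case 2, 3 of 10 shifted | Case 2, 4 of 10 shifted |
|---|---|---|---|---|
| 0.3 | 0.949 | 13.6% | 5.5% | 6.1% |
| 0.5 | 1.581 | 29.3% | 6.4% | 7.9% |
| 0.8 | 2.530 | 61.6% | 8.3% | 11.7% |
| 1.0 | 3.162 | 80.3% | 9.8% | 14.7% |

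The nominal rate is 5%. The two cases are the extremes of full return to habit and full retention of technique. The documents do not say where subjects will fall between them.

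**Contrasts between brushes.** Take the mean technique contribution to each brush, as a fraction of d:

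- Case 1: A, B and C each carry 1.0, so every difference is 0.
- Case 2, equal sequence sizes: each carries 1/3, so every difference is 0.
- Case 2, split 4/3/3 with the largest group starting on A: A carries 4/10 = 0.4, and B and C carry 3/10 = 0.3. Then A − C = A − B = 0.1 and B − C = 0.

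At most a tenth of the shift is left in a between-brush difference, against the whole of it in the within-brush change under Case 1.

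**The case against.** The strongest reply is that the question about bristle type is answered between brushes, and there the problem almost vanishes. All three test weeks share one instruction, C is labelled the control in Table 1, and section XVI plans a comparison among bristles. The primary outcomes are same-visit reductions and do not use the wash-out week as comparator. All of this stands. A reader might infer that the comparison of brushes, or the primary result, is confounded by technique. The documents do not support that.

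Second, every visit follows 24 hours without oral hygiene (section VII), so both scores are taken after the same regrowth interval. This may shrink a technique effect. It does not make the preceding weeks alike, and it may shrink a brush effect too.

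Third, subjects know Bass technique after Visit 2, so the contrast may fade in periods 2 and 3. This is why Case 1 is an upper end and not an estimate.

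A reader might also infer that self-monitoring and brushing time change with the brush. The diary cannot be counted. Section VII has it given at Visit 1 and kept throughout, Table 2 has it given at Visit 2 and collected at Visit 7, and sections X and XII tie it to the test week. Usual brushing time is unspecified, so a change in it is possible but not shown. Usual brushing in the run-in is an inference from Table 2 and the absence of instruction.

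Finally, nothing in the plan says that a within-brush change will be credited to the brush. But nothing prevents it, and the test is planned without any limit on its interpretation.

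**Conclusion.** The point holds for the within-brush one-week tests of secondary outcomes 1, 2 and 4. These tests mix the brush with technique and regimen and cannot by themselves show a brush effect on plaque or abrasion.

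The size cannot be fixed from the documents. For an assumed shift of 0.3 to 1.0 SD, the chance of a significant result with no brush effect runs from about 14% to 80% if the shift recurs each period, and from about 5% to 15% if it is confined to period 1. Quoting the first range alone would overstate the case, since retained training and the common abstention both pull downwards. The consequence is limited to how one-week results may be stated in a 10-subject proof-of-concept study.

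**What to change.** In section XVI, add two statements. First, one-week conclusions on plaque index, plaque area and gingival abrasion rest on the within-subject contrasts between brushes, with C as control. Second, the within-brush one-week tests are descriptive and are not evidence of a brush effect.

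The within-subject wording is needed because section XVI currently names two-sample tests (Student t, Wilcoxon rank sum) for the comparison among bristles. The technique effect cancels in the mean difference under either kind of test, but the contrast should be defined on each subject's own differences.

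The cost is two sentences and no change in conduct. The sponsor gives up a stand-alone efficacy or safety statement for a single brush at one week.

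Giving the same brushing instruction in the run-in and wash-out weeks would address the mixture at its source. It is an optional design choice, not a required correction: it would end the return to usual habits that the wash-out now provides, and it might lower plaque at the baselines.

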## **X. PRODUCT USE COMPLIANCE**

To demonstrate compliance with product use, each subject will complete a daily diary indicating the time of each brushing for the one-week duration of the study. The subjects will be requested to return their diary and assigned toothbrush at the end of the study period.

## **XI. RESTRICTIONS**

Subjects will be advised of the following restrictions during the study period:

- To avoid using other oral hygiene products throughout the study period.
- To avoid starting or changing treatments, medications including OTC drugs and supplements that potentially modify plaque accumulation for the duration of the study.
- To refrain from starting or changing habits (e.g. eating chewing gum) to potentially modify subject's plaque accumulation condition for the duration of the study.

## **XII. STUDY PROCEDURE**

### **Screening and Enrollment Visit (Visit 1)**

Potential subjects will be instructed to refrain from regular oral hygiene regimen for 24 hours and eating for 4 hours before the appointment in the study.

Male and female subjects will read and sign the informed consent prior to enrollment. Subjects will be asked about demographics, medical history, general health status and current medication usage, and the information will be recorded.

Plaque Index (Quigley and Hein) of a whole mouth will be evaluated to verify that the subjects meet the inclusion and exclusion criteria (average PI>2).

If the participants meet the study criteria, they will be assigned to one of three treatment groups randomly based on computer generated randomized numbers.

Subjects will be instructed to use a toothpaste and a toothbrush (for wash-out period) provided by the study staff until the next visit. The appointment of next visit will be scheduled within 7 days ± one day.

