### **Inclusion Criteria**

Individuals may be included in the study provided they meet all of the following inclusion criteria:

- Must have read, understood and signed an informed consent prior to being entered into the study.
- Must be 18 to 70 years of age, male or female.
- Have at least 20 natural or restored teeth.
- Must have average Plaque Index of Ramfjord teeth at baseline greater than 2 (Quigley and Hein) at screening.
- Agree not to have a dental prophylaxis or any other elective, non-emergency dental procedures (other than those provided during the study) any time during the study.
- Agree to refrain from regular oral hygiene regimen for 24 hours and eating for 4 hours before the appointment in the study.
- Agree to abstain from the use of any dental products other than those provided in the study.
- Agree to comply with the conditions and schedule of the study.

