### **Exclusion Criteria**

Individuals are not eligible for participation in this study if any of the following are noted:

- Physical limitations or restrictions that might preclude normal tooth brushing.
- Evidence of gross oral pathology
- Presence of severe gingivitis with 30 or more sites showing bleeding on probing.
- Evidence of major soft tissue lesions or trauma at the baseline visit as determined by the Investigator/Examiner.
- Chronic disease with concomitant oral manifestations
- Subjects who are currently undergoing, or require, extensive dental work, orthodontic treatment or periodontal surgery or orthodontic treatment in the preceding 3 months
- Currently using bleaching trays
- Eating disorders
- Recent history of substance abuse
- Smoking >10 cigarettes/day

Version 061020

- Participation in other clinical studies within 14 days of screening

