### **Visit4**

After a 1-week washout, subjects will return to the office to begin the second period of the

[figure not shown]
Version 061020

study, using the same study procedures and be assigned the alternate toothbrush as in Visit 2.

At the end of Visit 5 (examination for the second product) they will go through a 1 week wash out period and then return for Visit 6 (baseline for the third product).

Rustogi Modified Navy Plaque Index (Rustogi et al. J Clin Dent. 1992)

After disclosing dental plaque on teeth, the Rustogi Modified Navy Plaque Index (Navy PI) is evaluated as either present or absent (1 or 0) on each of the nine areas of the buccal and lingual tooth surfaces except for third molars. Whole tooth, marginal, and approximal areas are defined as shown below. Score of each area (from A to I) will be recorded for further assessments. In this study, the PI should be evaluated by only trained and calibrated examiners.

[figure not shown]

Gingival Abrasion Score (Van der Weijden et al. J Clin Periodontol. 2004)

After the gums were dried with compressed air, Mira-2-Ton® disclosing solution was applied for better visualization of areas where the surface of the oral epithelium had been abraded. The gingival tissues were divided into three areas: marginal (cervical free gingiva), interdental (papillary free gingiva) and mid-gingival (attached gingiva).

The lesions were assessed as small (<5 mm), medium (3-5 mm) and large (>5 mm) using a periodontal probe. Those lesions measuring between 2 and 3 mm were assigned a score of small or medium according to nearest mm mark on the probe.

Version 061020

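### The brush sequence is assigned at Visit 1, a week before the first test brush and before the Visit 2 eligibility recheck, so subjects can be lost after randomization with no test-brush data

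*Combined protocol and SAP*

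**What the plan says.** **Assignment.** Section XII, Screening and Enrollment Visit (Visit 1), says of participants who meet the study criteria: "they will be assigned to one of three treatment groups randomly based on computer generated randomized numbers".

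**The following week.** The same section continues: "Subjects will be instructed to use a toothpaste and a toothbrush (for wash-out period) provided by the study staff until the next visit". It then sets the interval: "The appointment of next visit will be scheduled within 7 days ± one day". No test brush is given at Visit 1.

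**Visit 2.** The Visit 2 text has staff update the criteria, medical history and medications. The examiner then scores plaque and gingival abrasion and is to "record the scores on the Case Report Form for the baseline information". Only after that is the assigned brush given out. Table 2 carries a row for "Update of Inclusion/Exclusion criteria", marked at Visit 2 and at every later visit. Section IX provides the assigned brush only to subjects who satisfy all the criteria.

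**An exclusion tied to baseline.** Section VI, Exclusion Criteria, lists: "Evidence of major soft tissue lesions or trauma at the baseline visit as determined by the Investigator/Examiner".

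**Consequences.** Section XIV discontinues a subject who, once entered, breaks an entry criterion. It also says that withdrawals are not made up. Section VI enrols 10 subjects, and Section VII aims for 10 completers. Section XVI defines no analysis set and does not say how to treat someone randomized but never given a test brush. Table 2 has no row for randomization.

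**The concern.** Randomization is usually placed as close as possible to the first use of the assigned product, so that anyone who drops out or proves ineligible beforehand never enters the randomized set. Here a week on common products separates the two, and an eligibility check falls at the end of that week. A subject who fails this check is already assigned to a sequence. Had the assignment waited, the same person would have been a screen failure and another volunteer could have been taken.

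With about 10 subjects, each such loss removes a tenth of the sample and yields nothing on any of the three brushes. It can also unbalance the three sequences. In this cyclic design the sequence sizes determine how often each brush is used in each period, and the tests named in Section XVI do not adjust for period.

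**Working it through.** **Order of events, read across the sections**

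| Step | When | Where |
|---|---|---|
| Criteria assessed, sequence assigned | Visit 1 | Section XII, Visit 1; Table 2 |
| Common wash-out brush and toothpaste | 7 days ± 1 | Section XII, Visit 1 |
| Criteria updated | Visit 2 | Section XII, Visit 2; Table 2 |
| Scores recorded as baseline | Visit 2 | Section XII, Visit 2 |
| First test brush given, if all criteria are met | Visit 2 | Sections IX and XII |

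No step between the first and last rows uses the assignment. A subject can therefore be randomized, fail at Visit 2 and never use a test brush.

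**Which visit is baseline.** The term is not defined. The Visit 2 scores are labelled baseline, and the Visit 4 text refers to "Visit 6 (baseline for the third product", so the visit that starts a product is called its baseline. Against this, the plaque inclusion criterion, "Must have average Plaque Index of Ramfjord teeth at baseline greater than 2", goes on to say that it is judged at screening. Visit 2 is the more natural reading of the soft-tissue exclusion. The point does not depend on it, because the Visit 2 update and the discontinuation rule already allow exclusion after randomization.

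**Scale.** The plan has no figure to reproduce: Section XVI states that no sample size calculation was done, and no dropout or failure rate is given. Let p be the assumed probability that a randomized subject fails at Visit 2, independently of the others. With 10 randomized, P(at least one loss) = 1 − (1 − p)^10, and the expected number lost is 10p.

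| Assumed p | P(at least one of 10 lost) | Expected number lost |
|---|---|---|
| 0.03 | 1 − 0.97^10 = 0.26 | 0.3 |
| 0.05 | 1 − 0.95^10 = 0.40 | 0.5 |
| 0.10 | 1 − 0.90^10 = 0.65 | 1.0 |

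Over a wider assumed range of 2% to 20%, the probability runs from 18% to 89%.

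**Sequence balance.** Ten subjects cannot be divided equally by three; the most even split is 4/3/3. If that split were achieved, which the plan does not guarantee, one loss would take 1/4 to 1/3 of a sequence and leave either 3/3/3 or 4/3/2. A loss can therefore unbalance the sequences, but it need not.

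**The case against.** The strongest reply is that the Visit 1 text randomizes only those who meet the study criteria, and that Table 2 places the full assessment at Visit 1 with only updates afterwards. On that reading eligibility is complete at randomization, and the lesion exclusion could be a Visit 1 check. A reader might infer that the protocol knowingly randomizes before eligibility is finished. The documents do not settle this, because the baseline visit is undefined. The Visit 2 text does still speak of potential subjects, but that sentence repeats the opening of the Visit 1 text and may simply have been carried over.

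Other parts of the reply also stand:

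- The update is marked at every visit through Visit 7. It is a continuing check, not one peculiar to Visit 2, and moving the assignment does nothing about later losses.
- A reader might infer that any new medicine during the wash-out week makes a subject ineligible. No inclusion or exclusion criterion concerns new medicines; Section XI only advises against starting or changing those that could affect plaque.
- Sequences of 3 or 4 are not promised. The plan gives no block size or allocation ratio.
- The no-replacement rule is written for withdrawn subjects. Whether it covers discontinued subjects is not stated.
- A reader might infer that the comparison of brushes is biased. Before Visit 2 everyone uses the same products, so no test brush can cause a loss. The examiner is blinded, and the staff responsible for assignment are blinded to product.

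None of this removes the avoidable loss. However baseline is defined, someone who fails at Visit 2 is already randomized, and the plan does not say how that person is counted.

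**Conclusion.** The point holds as a minor one. Assigning the sequence at Visit 1 gains nothing and exposes the study to losses after randomization but before any test brush. These losses sit badly with a target of 10 completers from 10 enrolled.

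The 26% to 65% chance of at least one loss rests wholly on an assumed 3% to 10% failure rate and on independence between subjects. It shows how small risks add up over 10 people and is not an estimate for this study. What is at stake is sample size, possibly sequence balance, and clarity about who is analysed. The validity of the comparison is not in question.

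**What to change.** Move the assignment sentence from the Visit 1 text to the Visit 2 text in Section XII. Place it after the eligibility update and the baseline oral check and immediately before the first test brush is distributed. Count anyone who fails before then as a screen failure, outside the 10 enrolled. Add a randomization row to Table 2, and state which visit is the baseline visit in the soft-tissue exclusion.

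The cost is small. No visit or procedure is added, though one or two more people may need screening. The meaning of enrolment in Section VI and in the Visit 1 text must be reworded to match. If the sponsor keeps assignment at Visit 1, the plan should at least state whether a subject excluded before the first test brush is replaced, and how that subject is treated in the analysis.
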